## 12.2.2 Efficacy analyses

Descriptive statistics by treatment group for the PAC-SYM total score and each domain score will be summarized at baseline, Weeks 4, 12, and 14 as well as the change from baseline to each post-dose time point. Descriptive statistics by treatment group for the PAC-QOL total score and each domain score will be summarized at baseline, Weeks 4, 12, and 14 as well as the change from baseline to each post-dose time point.

## 12.2.3 Health economics

Descriptive statistics for the frequency of responses for each of the 5 EQ-5D questions will be summarized by treatment group for baseline, Weeks 4, 12, and 14. The number and percentage of questionnaires completed at each visit will also be presented.

The percentage of patients with at least 1 healthcare visit will be summarized for each OIC healthcare utilization category (physician or other health care practitioner, urgent care center or hospital ER, inpatient hospital) by treatment group. The total number of visits and number of healthcare visits per patient year will be summarized by treatment group using descriptive statistics for each OIC healthcare utilization category. In addition, the reason for the visit (eg, enemas, manual disimpactions, treatment of anal fissures, treatment of bowel necrosis, and other) will also be summarized by treatment group using descriptive statistics.

## 12.2.4 Interim analyses

No interim analysis is planned.

# **12.3** Determination of sample size

No formal sample size calculation was performed for this long-term safety study. The sample size will be determined by the number of patients from the previous study D3820C00004 who enroll.

## 13.2 Overdose

For the NKTR-118 program, overdose is defined as a dose ingested (or taken via any other route), confirmed by the patient (if possible), in excess of the total daily dose specified for the patient in their treatment group of the protocol. All reports of overdose (with or without associated AEs) are to be collected.

No cases of overdose have been previously reported with NKTR-118. No specific antidote for overdose with NKTR-118 has been identified to date.

If a patient on opioid therapy receives an overdose with NKTR-118, the patient should be monitored closely for evidence of opioid withdrawal symptoms and reversal of central analgesic effect. In cases of known or suspected overdose, symptomatic treatment as well as monitoring of vital functions should be performed. In cases of severe intoxication, intensive care procedures are recommended. Close medical supervision and monitoring should be continued until the patient recovers.

For recording purposes:

- If an overdose is reported during the course of a study, the patient is evaluated by the investigator/site staff to determine whether an SAE, non-serious AE, or no symptoms have been experienced after the overdose has been taken.
- If the patient experiences an overdose with an associated SAE, the investigator/site staff will capture details of the SAE and associated information on OVERDOSE, AELOG, and SAE modules in the eCRF.
- If the patient experiences an overdose with an associated non-serious AE, the investigator/site staff will capture details of the non-serious AE and associated information on OVERDOSE and AELOG modules in the eCRF.
- If the patient experiences an overdose with no symptoms, the investigator/site staff will capture details of the overdose and associated information on OVERDOSE module only in the eCRF.
- The OVERDOSE module (found in Module Package Library) is the preferred way of collecting overdose information. If the OVERDOSE module cannot be used, for example, if a CRO is managing the study and is unable to use the module, the Clinical Study Overdose template, may be used. This form is also used if the overdose occurred in a person not enrolled in the study, eg, accidental ingestion by a relative of the patient.

#### For reporting purposes:

- If an overdose occurs in the course of an AstraZeneca study, the investigators/site staff inform appropriate AstraZeneca representatives immediately, but no later than the end of the next business day of when he or she becomes aware of it.
- The designated AstraZeneca representative or its representative works with the investigator to ensure that all relevant information is provided to the AstraZeneca Patient Safety Data Entry Site (DES).
- The following timelines will apply on reports of overdose:
  - Fatal/life-threatening SAEs are sent to DES within 1 calendar day of initial notification of the overdose.
  - Other SAEs are sent to DES within 4 calendar days of initial notification of the overdose.
  - Overdoses with no symptoms or with associated non-serious AEs are sent to DES within 5 calendar days of initial notification of the overdose.

## 13.3 Pregnancy

All outcomes of pregnancy should be reported to AstraZeneca or its representative on the pregnancy form. The outcomes of any conception occurring from the date of the first dose until 12 weeks after the date of last dose must be followed up and documented.

## 13.3.1 Maternal exposure

Requirements for contraception in WOCBP are specified in Inclusion Criterion #6 (see Section 4.1).

If a patient becomes pregnant during the course of the study, the IP should be discontinued immediately.

In clinical studies, when a study participant becomes pregnant, the PREGREP module is used to report the pregnancy, and the PREGOUT module is used to record the outcome.

Pregnancy itself is not regarded as an AE unless there is a suspicion that the IP under study may have interfered with the effectiveness of a contraceptive medication. Congenital abnormalities/birth defects, spontaneous miscarriages or ectopic pregnancy should be reported and handled as SAEs. Elective abortions without complications should not be handled as AEs. The outcome of all pregnancies (spontaneous miscarriage, elective termination, ectopic pregnancy, normal birth, or congenital abnormality) should be followed up and documented even if the patient was discontinued from the study. If any pregnancy occurs in the course of the study, then investigators or other site personnel must inform appropriate AstraZeneca representatives **within 1 day** ie, immediately, but no later than the **end of the next business day** of when he or she becomes aware of it.

The designated AstraZeneca representative works with the investigator to ensure that all relevant information is provided to the AstraZeneca Patient Safety data entry site within 1 or 5 days for SAEs, see Section 6.3.5 and within 30 days for all other pregnancies.

The same timelines apply when outcome information is available.

## 13.3.2 Paternal exposure

Male patients must refrain from fathering a child or donating sperm during the study and 12 weeks following the last dose, since the potential for chromosomal aberrations in male gametes, and possible teratogenic effects thereof, has not yet been thoroughly investigated. Male patients who are sexually active must use a barrier (condom with spermicide) method of contraception from the first dose of IP until 12 weeks after their last dose.

Pregnancy of the patients' partners is not considered to be an AE. However, the outcome of all pregnancies (spontaneous miscarriage, elective termination, normal birth, or congenital abnormality) must be followed up and documented. In addition, whenever possible, efforts should be made to complete the PREGREP and PREGOUT modules (see Section 13.3.1).

If any pregnancy occurs in the course of the study, then investigators or other site personnel must inform appropriate AstraZeneca representatives **within 1 day** ie, immediately, but no later than the **end of the next business day** of when he or she becomes aware of it.

The designated AstraZeneca representative works with the investigator to ensure that all relevant information is provided to the AstraZeneca Patient Safety data entry site within 1 or 5 days for SAEs, see Section 6.3.5 and within 30 days for all other pregnancies.

The same timelines apply when outcome information is available.

Appendix B Additional Safety Information

# FURTHER GUIDANCE ON THE DEFINITION OF A SERIOUS ADVERSE EVENT (SAE)

## Life threatening

'Life-threatening' means that the subject was at immediate risk of death from the AE as it occurred or it is suspected that use or continued use of the product would result in the subject's death. 'Life-threatening' does not mean that had an AE occurred in a more severe form it might have caused death (eg, hepatitis that resolved without hepatic failure).

## Hospitalisation

Outpatient treatment in an emergency room is not in itself a serious AE, although the reasons for it may be (eg, bronchospasm, laryngeal oedema). Hospital admissions and/or surgical operations planned before or during a study are not considered AEs if the illness or disease existed before the subject was enrolled in the study, provided that it did not deteriorate in an unexpected way during the study.

## Important medical event or medical intervention

Medical and scientific judgement should be exercised in deciding whether a case is serious in situations where important medical events may not be immediately life threatening or result in death, hospitalisation, disability or incapacity but may jeopardize the subject or may require medical intervention to prevent one or more outcomes listed in the definition of serious. These should usually be considered as serious.

Simply stopping the suspect drug does not mean that it is an important medical event; medical judgement must be used.

Examples of such events are:

- Angioedema not severe enough to require intubation but requiring iv hydrocortisone treatment
- Hepatotoxicity caused by paracetamol (acetaminophen) overdose requiring treatment with N-acetylcysteine
- Intensive treatment in an emergency room or at home for allergic bronchospasm
- Blood dyscrasias (eg, neutropenia or anaemia requiring blood transfusion, etc) or convulsions that do not result in hospitalisation
- Development of drug dependency or drug abuse.

# A GUIDE TO INTERPRETING THE CAUSALITY QUESTION

The following factors should be considered when deciding if there is a "reasonable possibility" that an AE may have been caused by the drug.

- Time Course. Exposure to suspect drug. Has the subject actually received the suspect drug? Did the AE occur in a reasonable temporal relationship to the administration of the suspect drug?
- Consistency with known drug profile. Was the AE consistent with the previous knowledge of the suspect drug (pharmacology and toxicology) or drugs of the same pharmacological class? OR could the AE be anticipated from its pharmacological properties?
- Dechallenge experience. Did the AE resolve or improve on stopping or reducing the dose of the suspect drug?
- No alternative cause. The AE cannot be reasonably explained by another aetiology such as the underlying disease, other drugs, other host or environmental factors.
- Rechallenge experience. Did the AE reoccur if the suspected drug was reintroduced after having been stopped? AstraZeneca would not normally recommend or support a rechallenge.
- Laboratory tests. A specific laboratory investigation (if performed) has confirmed the relationship?

A "reasonable possibility" could be considered to exist for an AE where one or more of these factors exist.

In contrast, there would not be a "reasonable possibility" of causality if none of the above criteria apply or where there is evidence of exposure and a reasonable time course but any dechallenge (if performed) is negative or ambiguous or there is another more likely cause of the AE.

In difficult cases, other factors could be considered such as:

- Is this a recognised feature of overdose of the drug?
- Is there a known mechanism?

Ambiguous cases should be considered as being a "reasonable possibility" of a causal relationship unless further evidence becomes available to refute this. Causal relationship in cases where the disease under study has deteriorated due to lack of effect should be classified as no reasonable possibility.

Clinical Study Protocol Appendix C		
Drug Substance	NKTR-118	
Study Code	D3820C00007	
Edition Number	1.0	
Date		

Appendix C International Airline Transportation Association (IATA) 6.2 Guidance Document

# LABELLING AND SHIPMENT OF BIOHAZARD SAMPLES

International Airline Transportation Association (IATA) classifies biohazardous agents into 3 categories (http://www.iata.org/whatwedo/cargo/dangerous\_goods/infectious\_substances. htm). For transport purposes the classification of infectious substances according to risk groups was removed from the Dangerous Goods Regulations (DGR) in the 46th edition (2005). Infectious substances are now classified either as Category A, Category B or Exempt. There is no direct relationship between Risk Groups and categories A and B.

**Category A Infectious Substances** are infectious substances in a form that, when exposure to it occurs, is capable of causing permanent disability, life-threatening or fatal disease in otherwise healthy humans or animals. Category A pathogens are eg, Ebola, Lassa fever virus:

• are to be packed and shipped in accordance with IATA Instruction 602.

**Category B Infectious Substances** are infectious substances that do not meet the criteria for inclusion in Category A. Category B pathogens are eg, Hepatitis A, B, C, D, and E viruses, Human immunodeficiency virus (HIV) types 1 and 2. They are assigned the following UN number and proper shipping name:

- UN 3373 Biological Substance, Category B
- are to be packed in accordance with UN3373 and IATA 650

**Exempt** - all other materials with minimal risk of containing pathogens

- Clinical trial samples will fall into Category B or exempt under IATA regulations
- Clinical trial samples will routinely be packed and transported at ambient temperature in IATA 650 compliant packaging (http://www.iata.org/whatwedo/cargo/dangerous\_goods/infectious\_substances. htm)
- Biological samples transported in dry ice require additional dangerous goods specification for the dry-ice content
- IATA compliant courier and packaging materials should be used for packing and transportation and packing should be done by an IATA certified person, as applicable

Clinical Study Protocol Appendix C Drug Substance NKTR-118 Study Code D3820C00007 Edition Number 1.0 Date

• Samples routinely transported by road or rail are subject to local regulations which require that they are also packed and transported in a safe and appropriate way to contain any risk of infection or contamination by using approved couriers and packaging / containment materials at all times. The IATA 650 biological sample containment standards are encouraged wherever possible when road or rail transport is used.

Clinical Study Protocol Appendix D		
Drug Substance	NKTR-118	
Study Code	D3820C00007	
Edition Number	1.0	
Date		

Appendix D Child-Pugh Classification

## 1. CRITERIA FOR CHILD-PUGH CLASSIFICATION

	Points Scored for Observed Findings		
	1	2	3
Encephalopathy grade*	none	1 or 2	3 or 4
Ascites	absent	slight	moderate
Serum bilirubin, mg/dL	<2	2 to 3	>3
Serum albumin, g/dL	>3.5	2.8 to 3.5	<2.8
Prothrombin time, sec prolonged	<4	4 to 6	>6

#### Table 1Criteria for Child-Pugh Classification

\*Grade 0: normal consciousness, personality, neurological examination

Grade 1: restless, sleep disturbed, irritable/agitated, tremor, impaired handwriting

Grade 2: lethargic, time-disoriented, inappropriate, asterixis, ataxia

Grade 3: somnolent, stuporous, place-disoriented, hyperactive reflexes, rigidity

Grade 4: unrousable coma, no personality/behavior, decerebrate

Mild=5 or 6 points; Moderate=7 to 9 points; Severe =10 to 15 points

# Appendix E Morphine Equivalents Conversion Chart

## 1. MORPHINE EQUIVALENTS CONVERSION CHART

Oral Dose (mg)	Analgesic	Parenteral Dose (mg)	Oral Morphine Equivalents (mg)
15	Morphine	5	15
100	Codeine	60	15
-	Fentanyl a	0.1 (intravenous)	15
10	Hydrocodone	-	15
4	Hydromorphone	1.5	15
2	Levorphanol	1	15
150	Meperidine	50	15
5	Methadone	5	15
10	Oxycodone	-	15
5	Oxymorphone	1	15
100	Propoxyphene	-	15
60	Tapentadol	-	15
67.5	Tramadol	-	15

#### Table 1Dose Equivalents for Opioid Analgesics

Note: All doses listed in the above chart will be regarded as equianalgesic. For example, 10 mg of oral hydrocodone corresponds to 15 mg of oral morphine equivalents. And one mg of parenteral oxymorphone is considered to be equivalent to 15 mg of oral morphine.

For the 72 hr fentanyl patch (25 μg/hr), the equianalgesic daily dose of oral morphine will be considered to be 15 mg every 4 hh OR 45 mg BID of MS-Contin (i.e., 90 mg/day of morphine). For transmucosal fentanyl (i.e., the fentanyl "lollipop"), an 800 μg dose will be regarded as equivalent to 30 mg of oral morphine.

Clinical Study Protocol Appendix F		
Drug Substance	NKTR-118	
Study Code	D3820C00007	
Edition Number	1.0	
Date		

# Appendix F Highly Effective Forms of Birth Control

## 1. HIGHLY EFFECTIVE FORMS OF BIRTH CONTROL

- 1. Total sexual abstinence (for the total duration of the trial including the followup period)
- 2. Vasectomized sexual partner (with participant assurance that partner received post-vasectomy confirmation of azoospermia)
- 3. Tubal occlusion
- 4. Intra-uterine Device (provided that coils are copper-banded)
- 5. Levonorgestrel Intrauterine System (e.g. Mirena)
- 6. Medroxyprogesterone injections (Depo-Provera)
- 7. Etonogestrel implants (Implanon, Norplan)
- 8. Normal and low dose combined oral pills
- 9. Norelgestromin / ethinylestradiol transdermal system
- 10. Intravaginal device (e.g., ethinylestradiol and etonogestrel)
- 11. Cerazette (desogestrel)

In addition to the use of a highly effective form of birth control, WOCBP are instructed to use a barrier method of contraception during sexual intercourse (female or male condom).

The following methods are considered **NOT** to be highly effective and are therefore not acceptable contraceptive methods in NKTR-118 trials

- 1. Triphasic combined oral contraceptives
- 2. All progesterone only pills, except Cerazette
- 3. All barrier methods, if intended to be used alone
- 4. Non-copper containing IUDs
- 5. Fertility awareness methods
- 6. Coitus interruptus

Clinical Study Protocol Appendix G		
Drug Substance	NKTR-118	
Study Code	D3820C00007	
Edition Number	2.0	
Date		

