### **Duration of treatment**

The study duration will be up to 14 weeks, consisting of a 12-week treatment period, and a follow-up visit 2 weeks after the last dose of study drug.

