## 3.1 Overall study design and flow chart

This is a 12-week extension of the Phase III, multi-center, double-blind, randomized, placebo-controlled, parallel group 12-week study D3820C00004 to evaluate the safety and tolerability of NKTR-118 12.5 and 25 mg and placebo in the treatment of OIC in patients with non-cancer-related pain. This will be a study with global participation that may include the following countries: Australia, Belgium, Canada, Croatia, the Czech Republic, France, Germany, Hungary, Israel, Slovakia, Spain, the United Kingdom (UK), and the United States (US). Patients will continue on their randomized doses from the D3820C00004 study without unblinding. The study duration will be up to 14 weeks, consisting of a 12-week treatment period, and a follow-up visit 2 weeks after the last dose of study drug. Patients who successfully complete the 12-week treatment period may be eligible to participate in a 52-week long-term safety extension study. Up to 630 randomized patients could potentially participate in this study.

Patients will sign the informed consent at the enrollment visit (Visit 1), which will correspond with the last treatment visit in the previous study D3820C00004. Assessments at Visit 1 will be similar to those at the last treatment visit in the previous study.

To be eligible for the current study, patients must continue to fulfill all inclusion/exclusion (I/E) requirements of study D3820C00004. Demographics, medical and surgical history, and laxative tolerance status will be obtained from study D3820C00004.

Unlike study D3820C00004, the present study will not utilize an eDiary device. The NRS for pain will be completed on a SitePad device at the clinic. Use of bisacodyl as a rescue medication will be assessed by pill count of returned bisacodyl at study visits. In addition, to facilitate the collection of breakthrough pain opioid use, and any newly prescribed concomitant medication use, patients will be provided with a home diary to record such medication usage between visits.

The first dose of study drug in the current study will be taken by the patient at home on Day 2 (on Day 1 patients will have taken their last dose of study drug for study D3820C00004).

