#### 3.1.2.2 Visit 4 (Week 12, Day 85)

Visit 4 will occur on Day 85 ( $\pm$ 3 days), and will be scheduled in the morning. If a patient who plans to enter the 52-week safety extension study accidentally takes study drug at home on the morning of Visit 4, the patient should be rescheduled to return the next morning for all Visit 4 procedures. If a patient accidentally takes study drug at home on the morning of Visit 4 but does not intend to participate in the 52-week safety extension study, he/she can proceed with Visit 4.

For patients who enter the 52-week safety extension study, Visit 4 will also correspond to the randomization visit for the 52-week safety extension study. The order of procedures will be different for patients who enter the 52-week safety extension study (and the order noted for the safety extension study should be followed). However, all Visit 4 assessments listed below are to be collected, even if not required for the 52-week safety extension study.

At Visit 4 the following procedures will be performed:

- PAC-SYM will be completed.
- PAC-QOL will be completed.
- EQ-5D will be completed.
- Pain level (NRS) (average pain over the previous 7 days) will be recorded.
- OIC Healthcare Resource Utilization questionnaire will be completed.
- Physical examination including weight, body temperature, and respiratory rate will be performed. This may include optional rectal examination at investigator discretion unless patients enter the safety extension study; a rectal examination is mandatory for patients who enter the safety extension study.

- Sitting blood pressure and pulse must be measured. Please see Section 6.3.13.1 for additional details on the protocol-mandated methods for collection of vital signs. The accurate time in date, hours and minutes will be recorded for this measurement.
- Triplicate 12-lead ECG will be obtained.
- Blood samples will be collected for laboratory assessments (clinical chemistry [including total cholesterol] and hematology) and serum pregnancy test (WOCBP).
- A urine sample will be collected for the following: urine drug screen (urine toxicology) and U/A.
- C-SSRS to assess suicidal risk, ideation, and behavior will be completed.
- Daily maintenance and breakthrough pain opioid dosing regimens will be asked about and recorded on the appropriate eCRFs.
- Use of enema medication since Visit 3 will be asked about and recorded on the enema eCRF.

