#### 3.1.3 Final Visit (Visit 5, Week 14, Day 99)

Visit 5 will occur on Day 99 ( $\pm$ 3 days). At Visit 5, the following procedures will be performed:

- PAC-SYM will be completed.
- PAC-QOL will be completed.
- EQ-5D will be completed.
- OIC Healthcare Resource Utilization questionnaire will be completed.
- Sitting blood pressure and pulse must be measured. Please see Section 6.3.13.1 for additional details on the protocol-mandated methods for collection of vital signs. The accurate time in date, hours and minutes will be recorded for this measurement.
- Single 12-lead ECG will be obtained.
- Blood samples will be collected for laboratory assessments (clinical chemistry and hematology) and serum pregnancy test (WOCBP).
- C-SSRS to assess suicidal risk, ideation, and behavior will be completed.
- Daily maintenance and breakthrough pain opioid dosing regimens will be asked about and recorded on the appropriate eCRFs.
- Use of enema rescue medication since Visit 4 will be recorded.
- Use of concomitant medication (including bisacodyl and other laxative medication with the exception of enema) since Visit 4 will be recorded.
- AEs since Visit 4 will be recorded.

# Table 1

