### 4.1 Inclusion criteria

For inclusion in the study, patients should fulfill the following criteria:

- 1. Must have completed the 12-week study D3820C00004 through Visit 8
- 2. Provision of written informed consent prior to any study-specific procedures
- 3. Men and women who were between the ages of  $\geq 18$  and < 85 years at the time of the screening visit for study D3820C00004
- 4. Continuing to receive a stable maintenance opioid regimen consisting of a total daily dose of 30 mg to 1000 mg of oral morphine, or equianalgesic amount(s) of 1 or more other opioid therapies (see Appendix E)
- 5. Willingness to continue abstinence from all laxatives and other bowel regimens including prune juice and herbal products throughout this additional 12-week treatment period, and to use only bisacodyl as rescue medication if a BM has not occurred within at least 72 hours of the last recorded BM
- 6. Male patients who are sexually active must continue to use a double-barrier method of contraception (condom with spermicide) until 12 weeks after their last dose of investigational product (IP). Women of childbearing potential must have a negative pregnancy test and confirmed (by the investigator) continue to use a highly effective form of birth control until 12 weeks after their last dose. Highly effective forms of birth control are listed in Appendix F. Women of non-childbearing potential can

participate in this study without adherence to the pregnancy precautions. Women of non-childbearing potential are defined as women who are either permanently sterilized (hysterectomy or bilateral oophorectomy or bilateral salpingectomy) or are postmenopausal. Any woman who is older than 57 years of age is considered postmenopausal. In addition, women who are older than 50 years of age and amenorrheic with at least 12 months having passed since the last menses (after cessation of all exogenous hormone treatments), are also considered postmenopausal.

- 7. Continue to be able to understand and comply with the requirements of the study, as judged by the investigator (includes ability to read and write and use the Sitepad device)
- 8. Outpatient status at enrollment

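### Appendix F gives abstinence an end point about 10 weeks earlier than the 12 weeks after last dose that inclusion criterion 6 requires (minor safety-wording inconsistency)

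*Protocol*

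**What the plan says.** Protocol Section 4.1, criterion 6, requires that women of childbearing potential "continue to use a highly effective form of birth control until 12 weeks after their last dose", and then states: "Highly effective forms of birth control are listed in Appendix F". Section 13.3.1 (maternal exposure) refers back to criterion 6 for the contraception requirements. Section 13.3 uses the same limit, calling for follow-up of any conception from first dose to 12 weeks after the last.

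Appendix F lists 11 methods. Ten are named without a duration. Item 1 has one: "Total sexual abstinence (for the total duration of the trial including the followup period".

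On the length of the study, Section 3.1 says "The study duration will be up to 14 weeks, consisting of a 12-week treatment period", and the synopsis completes this with "a follow-up visit 2 weeks after the last dose of study drug". Section 3.1.2.2 says "Visit 4 will occur on Day 85" and Section 3.1.3 says "Visit 5 will occur on Day 99", each with a window of 3 days either way. Section 5.5.2 has dosing on Days 2 to 85. Patients who enter the 52-week safety extension do not attend Visit 5.

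**The concern.** Criterion 6 sets how long contraception must last, and Appendix F says which methods count. For abstinence alone, the list also states a stopping point, and it is not the one in the criterion. A member of site staff who counsels from the appendix could tell a woman relying on abstinence that her obligation ends at Visit 5. That is in literal agreement with item 1 and contrary to criterion 6.

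What is at stake is participant safety, namely possible fetal exposure in a window that the sponsor chose to protect. The 12-week limit appears in criterion 6, in Section 13.3 and in Section 13.3.2, so item 1 is the outlier. The last scheduled pregnancy test is at Visit 5, and no planned test would pick up a conception in the weeks after it. Nothing in the statistical analysis depends on this.

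**Working it through.** **Inputs**
- Required end of contraception: last dose + 12 weeks = 12 × 7 = 84 days (Section 4.1, criterion 6).
- Last dose: Day 85 for a patient who completes treatment (Section 5.5.2).
- Final visit: Day 99, allowed range Day 96 to Day 102 (Section 3.1.3).
- End of item 1: the end of the trial with its follow-up period (Appendix F).

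**1. The protocol's own duration reproduces.** 12 weeks of treatment + 2 weeks of follow-up = 14 weeks. In days, 99 − 85 = 14 days = 2 weeks.

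**2. What follow-up means in this protocol.** The term in item 1 is not formally defined, but usage elsewhere is consistent. Section 3.1 calls Visit 5 the follow-up visit, Section 6.3.4 collects adverse events up to that same visit, and Section 6.3.10 labels Week 14 as follow-up. No section describes a follow-up period that reaches 12 weeks after last dose. Section 13.3.2 points the same way for men: "Male patients must refrain from fathering a child or donating sperm during the study and 12 weeks following the last dose". It names the study and the 12 weeks as two separate periods.

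**3. Size of the mismatch.**
- Nominal: item 1 ends 99 − 85 = 14 days after last dose, so the mismatch is 84 − 14 = 70 days = 10 weeks.
- Early Visit 5: 96 − 85 = 11 days, mismatch 84 − 11 = 73 days.
- Late Visit 5: 102 − 85 = 17 days, mismatch 84 − 17 = 67 days.
- In calendar terms, criterion 6 runs to Day 85 + 84 = Day 169, and item 1 runs to about Day 99.

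**4. Sensitivity to the last-dose date.** Visit 4 may fall on Day 82 to Day 88. Because patients hold the morning dose for that visit (Section 3.1.1), the last dose may be on the visit day or the day before.
- Last dose on the Visit 4 day: 96 − 88 = 8 to 102 − 82 = 20 days, mismatch 64 to 76 days.
- Last dose the day before: 96 − 87 = 9 to 102 − 81 = 21 days, mismatch 63 to 75 days.

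The extremes are 63 to 76 days. They require Visits 4 and 5 to move in opposite directions, away from the planned two-week interval, so 67 to 73 is the more useful range.

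**5. Alternative reading of the trial's end.** Section 9.5 defines the end of the study by the last visit of the last patient. Read that way, item 1 has no fixed length. It reaches the required date only if last dose + 84 days falls on or before the last patient's last visit, that is, if the woman's own Visit 5 is at least 84 − 14 = 70 days before it. Neither reading guarantees the 12 weeks.

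**The case against.** The strongest reply is that criterion 6 controls. It fixes the period and uses Appendix F only to say which methods qualify, and Section 13.3.1 names criterion 6 as the place where the requirement stands. The two texts can both be obeyed: a woman who meets criterion 6 also meets item 1. If she ends abstinence after Visit 5, she must change to another listed method, with the barrier method that the appendix adds, until week 12. This stands, and it limits the point to an inconsistency of wording.

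A reader might go further and infer that the protocol leaves these women without a contraception requirement for 10 weeks. The documents do not support that. The 70 days are the distance between two statements, and they become a real gap only if a site overlooks the criterion that led it to the appendix. Nor should a reader infer that pregnancies in that window would go unrecorded: Section 13.3 requires follow-up of conceptions to 12 weeks after last dose, and Section 13.3.1 continues this for patients who have discontinued.

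It can also be argued that the words in item 1 describe the method, separating sustained abstinence from the fertility-awareness methods that the same page rejects. That is plausible as to motive, but the text still states an end point, and it does so for this method only. The reply that follow-up is undefined is correct but does not rescue the wording, since no section supplies a 12-week meaning. Finally, consent material is not part of the public copy, so what patients were told cannot be checked.

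**Conclusion.** The inconsistency is real and minor. Item 1 of Appendix F ends abstinence nominally 70 days (67 to 73 with the Visit 5 window) before the date that criterion 6 and the conception window in Section 13.3 set.

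The figure assumes that the last dose is on Day 85 and that the follow-up period in item 1 closes with Visit 5, as the rest of the protocol uses the term. Under the Section 9.5 reading the mismatch varies by patient and may be nil for some. The study dates are not visible, so that share cannot be worked out.

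Harm requires a site to counsel from Appendix F alone. It is confined to women of childbearing potential who rely on abstinence and do not enter the 52-week study, and the protocol gives no number for them. Criterion 6 remains in force, and no estimate, analysis set or summary is touched. The correction is worth making because the subject is possible fetal exposure and the cost is close to nothing.

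**What to change.** Reword Appendix F item 1 to: *Total sexual abstinence (throughout the study and until 12 weeks after the last dose of study drug)*. This keeps the on-study obligation explicit and brings the mismatch to 0 days. It is a one-line change with no new visit, test or data item.

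Optional and of less weight: the next-business-day notification clauses in Sections 13.3.1 and 13.3.2 are tied to pregnancies arising while the study is running, so it is unclear whether they apply after Visit 5. Extending them to conceptions up to 12 weeks after last dose would match Section 13.3. The cost is one phrase in each section and perhaps a few late reports to process. It adds little, because outcome follow-up for these pregnancies is already required.
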